7 EFFICACY ASSESSMENTS

In addition to the efficacy assessments listed below, this study plans to validate an in silico NASH disease model that predicts responders and nonresponders to EYP001a.

7.1 Efficacy Variables

7.1.1 Primary Efficacy Variables

The primary efficacy variable is absolute change in LFC as measured by MRI-PDFF from baseline to Week 12.

7.1.2 Secondary Efficacy Variables

The secondary efficacy variables include the following:

- Proportion of patients with $\geq 5\%$ absolute reduction in LFC as measured by MRI-PDFF from baseline to Week 12
- Proportion of patients with $\geq 10\%$ absolute reduction in LFC as measured by MRI-PDFF at Week 12
- Proportion of patients with $\geq 20\%$ absolute reduction in LFC as measured by MRI-PDFF at Week 12
- Proportion of patients with a relative reduction in LFC $\geq 20\%$ as measured by MRI-PDFF at Week 12
- Proportion of patients with a relative reduction in LFC $\geq 30\%$ as measured by MRI-PDFF at Week 12
- Percent change (relative reduction) in LFC as measured by MRI-PDFF from baseline to Week 12
- Change and percent change in imaging-derived mean cT1 from baseline to Week 12
- Change and percent change in WHR from baseline to Week 12 (Part B only)
- Change and percent change in WHtR from baseline to Week 12 (Part B only)
- Change in the following biomarkers of liver fibrosis and inflammation: ALT, AST, AST/ALT ratio, adiponectin, high sensitivity C-reactive protein, interleukin 6, tumor necrosis factor alpha, cytokeratin-18, fibronectin, hyaluronic acid, procollagen type III N-terminal peptide, tissue inhibitor of metalloproteinases-1 (and derived enhanced liver fibrosis score), Pro-C3, and chitinase-3-like protein 1 (also known as YKL-40) from baseline to Week 4, Week 8, and Week 14/ET, as applicable

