1.1 Rationale

The purpose of this Phase 2a study is to assess the effects of EYP001a compared with placebo on markers of LFC, inflammation, and fibrosis with respect to safety, tolerability, pharmacokinetics (PK), pharmacodynamics (PD), and lipid/metabolic profiles in patients with NASH with likely stage F2 to F3 fibrosis.

EYP001a Phase 1 data in healthy subjects showed that EYP001a was well tolerated after single and multiple oral administration from 30 to 800 mg (single ascending dose) and from 60 to 500 mg (multiple ascending dose). After single administration of EYP001a up to 500 mg, maximum observed plasma concentration (C_{max}) and area under the plasma concentration-time curve (AUC) from time 0 to infinite time seemed linear, but increased less than proportionally at the single-dose

level of 800 mg. After multiple administrations, C_{max} and AUC increased less than proportionally to the dose. In general, C_{max} and AUC were lower after repeated administrations compared to single administration. EYP001a elimination was on average fast: apparent elimination half-life associated with the terminal slope of the semilogarithmic EYP001a concentration-time curve was around 2 to 3 hours, with a tendency for faster elimination after multiple dosing. In 11 patients with chronic HBV infection randomized to 4 cross-over single-dose oral treatment periods receiving 300 mg EYP001a fasted or fed, either in the morning or evening, the relative EYP001a bioavailability and FXR-related PD were assessed. EYP001a PK in HBV patients seemed to be slightly influenced by food, with a delay of a few hours (ie, time to reach C_{max} [T_{max}]) in the absorption process, leading to a lower C_{max} . EYP001a exposure (ie, AUC) appeared to be higher under food conditions, but the variability of EYP001a PK and the small number of patients ($n = 11$) prevented a demonstration of bioequivalence on C_{max} , AUC from time 0 to the time of the last quantifiable concentration, and AUC. Finally, for all dosing conditions, despite similar rapid EYP001a elimination, FGF19 and 7 α hydroxy-4-cholesten-3-one (C4) showed a prolonged FXR target engagement over at least 24 hours, which was not influenced by fasting or fed condition or by morning or evening administration.

Figure 1. Effects of Food Intake on EYP001a Pharmacokinetic Parameters

[figure not shown]

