6.3.3.5 Day 56 (Week 8)

The following procedures will be performed at Day 56 (Week 8):

- Record changes in concomitant medications.
- Perform brief physical examination.
- Measure body weight and calculate BMI.
- Measure waist and hip circumferences.
- Calculate WHR and WHtR.

- Collect vital signs (systolic and diastolic blood pressure, heart rate, respiratory rate, and body temperature) with the patient in the sitting position after 5 minutes of rest and before any blood draws.
- Administer the AUDIT-C test.
- Counsel on diet/lifestyle.
- Collect blood sample for the following:
 - Chemistry, hematology, coagulation, and lipid and metabolic profile.
 - Sparse PD (predose [fasting]).
 - Liver fibrosis and inflammation.
 - Sparse PK (predose [fasting]).
 - Plasma storage.
- Collect urine sample for urinalysis and pregnancy test. If the pregnancy test is positive, perform serum hCG test.
- Perform 12-lead ECG.
- Assess adverse events.
- Collect returned used/unused study drug and assess compliance.
- Dispense new study drug and provide dosing instructions.

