6.3.3.7 Day 84 (Week 12)

The following procedures will be performed at Day 84 (Week 12):

- Record changes in concomitant medications.
- Perform brief physical examination.
- Measure body weight and calculate BMI.
- Measure waist and hip circumferences.
- Calculate WHR and WHtR.

- Collect vital signs (systolic and diastolic blood pressure, heart rate, respiratory rate, and body temperature) with the patient in the sitting position after 5 minutes of rest and before any blood draws.
- Administer the AUDIT-C test.
- Counsel on diet/lifestyle.
- Collect blood sample for the following:
 - Chemistry, hematology, coagulation, and lipid and metabolic profile.
 - Sparse PD (predose [fasting]).
 - Sparse PK (predose [fasting]).
 - Plasma storage.
- Collect urine sample for urinalysis and pregnancy test. If the pregnancy test is positive, perform serum hCG test.
- Perform 12-lead ECG.
- Perform MRI-PDFF and cT1 imaging.
- Perform FibroScan VCTE (optional).
- Assess adverse events.
- Collect returned used/unused study drug and assess compliance.

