6.5 Early Termination Visit and Withdrawal Procedures (Parts A and B)

The end of treatment for patients completing the study is Day 84 (Week 12).

Patients who discontinue early from the study for any reason before completion of the Treatment Period will be requested to return to the clinic for an ET Visit within a maximum of 48 hours after their last intake of study drug, regardless of how many days they participated in the study.

Patients who discontinue early from the study for any reason after completion of the Treatment Period and before the EOS Follow-up Visit will be requested to return to the clinic for an ET Visit as soon as possible and no later than the planned EOS Follow-up Visit.

For patients who are withdrawn from the study prior to completion, all ET procedures will be performed at an ET Visit. These procedures include the following:

- Record changes in concomitant medications.
- Perform brief physical examination.
- Measure body weight and calculate BMI.
- Measure waist circumference (Part A only).
- Measure waist and hip circumferences (Part B only).
- Calculate WHR and WHtR (Part B only).
- Collect vital signs (systolic and diastolic blood pressure, heart rate, respiratory rate, and body temperature) with the patient in the sitting position after 5 minutes of rest and before any blood draws.
- Administer the AUDIT-C test.
- Counsel on diet/lifestyle.
- Collect blood sample for the following:
 - Chemistry, hematology, coagulation, and lipid and metabolic profile.
 - PD (preferably within 24 to 48 hours of last intake of study drug).
 - Liver fibrosis and inflammation.
 - Serum pregnancy test.

- PK (preferably within 24 to 48 hours of last intake of study drug).
- Plasma storage.
- Collect urine sample for urinalysis.
- Perform 12-lead ECG.
- Perform MRI-PDFF and cT1 imaging only for patients on study drug ≥ 4 weeks.
- Perform FibroScan VCTE (optional).
- Assess pruritus (Part A only).
- Assess adverse events.
- Collect returned used/unused study drug and assess compliance.

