 - bb. At screening and on Days 1, 14, 28, 56, and 84; and at the EOS and ET Visits, plasma from blood samples will be stored for protocol-related safety testing or exploratory analyses.
 - cc. On Days 14, 28, 42, 56, 70, and 84, compliance will be assessed and study drug will be returned. In addition, on Days 14, 28, 42, 56, and 70 new study drug will be dispensed and dosing instructions provided.

ALT = alanine aminotransferase; AST = aspartate aminotransferase; AUDIT = Alcohol Use Disorders Identification Test; AUDIT-C = Alcohol Use Disorders Identification Test-Concise; BMI = body mass index; C4 = 7 α hydroxy-4-cholesten-3-one; CAP = controlled attenuation parameter; CDCA = chenodeoxycholic acid; cT1 = iron-corrected T1; DCA = deoxycholic acid; ECG = electrocardiogram; eCRF = electronic case report form; EOS = End of Study; ET = Early Termination; FGF19 = fibroblast growth factor 19; FUP = Follow-up; HBV = hepatitis B virus; hCG = human chorionic gonadotropin; HCV = hepatitis C virus; HIV = human immunodeficiency virus; LCA = lithocholic acid; LFC = liver fat content; LSM = liver stiffness measurement; MRI-PDFF = magnetic resonance imaging proton density fat fraction; PD = pharmacodynamic; PK = pharmacokinetic; RNA = ribonucleic acid; VCTE = vibration-controlled transient elastography; WHR = waist to hip ratio; WHtR = waist to height ratio.

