2.1.2 Secondary Objectives and Endpoints

Secondary Objective	Endpoint
To explore the pharmacokinetics (PK) of EYP001a	EYP001a concentrations
To evaluate pharmacodynamic (PD) effects of EYP001a on bile acid-related markers as appropriate	Plasma levels of: 
• 7a-hydroxy-4-cholest-3-one;• fibroblast growth factor 19;• and total, primary, and secondary bile acids (such as
◦ chenodeoxycholic acid,◦ deoxycholic acid,◦ lithocholic acid,◦ and/or others as appropriate).
To assess the effects of EYP001a on lipid and metabolic profiles	
• Branched-chain amino acid concentrations• Hemoglobin A1c (HbA1c)• Homeostatic model assessment for insulin resistance (morning fasting glucose and insulin)• Lipoprotein insulin resistance index by nuclear magnetic resonance based on serum
◦ cholesterol,◦ high-density lipoprotein cholesterol,◦ low-density lipoprotein (LDL) cholesterol,◦ triglycerides,◦ apolipoprotein B,◦ small dense-LDL, and◦ lipoprotein(a)• Lipoprotein particle size• Small LDL particle number• Small very low-density lipoprotein (VLDL) particle number• VLDL size
To assess the safety of EYP001a with statin coadministration	Safety and tolerability assessments will include the monitoring of

Secondary Objective	Endpoint
	
adverse events (AEs);AEs of special interest (AESIs) (i.e.,
pruritus [Part A only],drug-induced liver injury [Part A only],elevation of transaminases [Part B only],andall muscle-related AEs);serious AEs (SAEs); and findings fromphysical examinations,vital signs,electrocardiograms (ECGs), andclinical laboratory parameters.
To assess the effects of EYP001a on noninvasive biomarkers of liver fibrosis and inflammation	
Change from baseline to Week 4, Week 8, and Week 14/ET, as applicable, in the following biomarkers of liver fibrosis and inflammation:
 
Alanine aminotransferase (ALT),Aspartate aminotransferase (AST),AST/ALT ratio,adiponectin,high sensitivity C-reactive protein (hs-CRP),interleukin 6,tumor necrosis factor alpha,cytokeratin-18,fibronectin,hyaluronic acid,procollagen type III N-terminal peptide,tissue inhibitor of metalloproteinases-1 (and derived enhanced liver fibrosis [ELF] score),Pro-C3, andchitinase-3-like protein 1 (also known as YKL-40)

Additional secondary efficacy variables include the following:

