5 CHANGES FROM PROTOCOL-SPECIFIED STATISTICAL ANALYSES

For Part B analysis of LFC as measured by MRI-PDFF, the ANCOVA model specified in the Protocol includes both baseline LFC as a covariate and LFC stratification (3 categories) as a factor. Since this is redundant information, LFC stratification as a factor will be dropped as a covariate from the model; baseline LFC as a covariate is sufficient.

After Part A analysis was completed, the Per-Protocol Population definition was updated to require subjects to finish the 12-week Treatment Period. However, this part of the definition is excluded for analysis. Instead, the Part B Per-Protocol Population is clarified to require $\geq 60\%$ study drug compliance.

There are some other minor changes from the protocol-specified statistical analyses detailed in this SAP:

- Week 12 included for biomarkers of liver fibrosis and inflammation, as appropriate;
- Study endpoints and definition of mITT Population updated to clearly allow patients with ET assessments (not just Week 12 assessments) to be included.
- HbA1c is not analyzed at Week 2 and Week 12 with the other lipid and metabolic profile parameters.

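### In Part B, most fibrosis and inflammation markers have no planned end-of-treatment value in completers, because the panel is not drawn on Day 84 (Week 12)

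*Protocol*

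**What the plan says.** Protocol 7.1.2 lists 14 blood markers of liver fibrosis and inflammation, plus an ELF score derived from some of them, to be assessed "from baseline to Week 4, Week 8, and Week 14/ET, as applicable". The endpoint table in SAP 2.1.2 has the same time points: "Change from baseline to Week 4, Week 8, and Week 14/ET, as applicable, in the following biomarkers of liver fibrosis and inflammation". Protocol 2.2 makes the effect on these markers a secondary objective.

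Protocol 6.5 sets the end of treatment for completers at Day 84. The Part B blood list for that visit (6.3.3.7) has "Chemistry, hematology, coagulation, and lipid and metabolic profile", sparse PD, sparse PK and plasma storage, but no fibrosis and inflammation panel. Table 8, footnote bb, provides for stored plasma that day: "At screening and on Days 1, 14, 28, 56, and 84; and at the EOS and ET Visits, plasma from blood samples will be stored". Its stated uses are safety testing and exploratory analyses.

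SAP Section 5 lists as a change from the Protocol: "Week 12 included for biomarkers of liver fibrosis and inflammation, as appropriate". The visit windows in SAP 3.1.4 put ALT, AST and their ratio in Group I and hs-CRP in Group II, both with a Week 12 window. All the other markers are in Group III, together with HbA1c, and Group III has no Week 12 window.

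**The concern.** The primary endpoint (LFC) and cT1 are both read at Week 12. The natural question for the blood markers is what 12 weeks of treatment does to them and whether that agrees with the imaging. For most of them the schedule gives no value at that point. Week 8 is on drug but early. Week 14 is off drug.

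The consequence is one of interpretation. If an active arm separates from placebo at Week 8 and not at Week 14, or at neither, the data cannot show whether there was no effect at the end of treatment or one that faded within two weeks of stopping.

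The SAP adds a smaller problem. It announces Week 12 for these biomarkers, but its windows leave Group III without one, so some samples that are taken have no analysis visit.

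**Working it through.** The plan gives no figure of its own on this point, and its sample-size numbers do not bear on it. The check compares the visit lists with the windows and counts markers and days.

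**1. Where the panel is drawn in Part B** (Protocol 6.3.3.1 to 6.3.3.7, 6.4, 6.5)

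| Visit | Panel listed? |
|---|---|
| Day 1 | yes |
| Day 14 | no |
| Day 28 | yes |
| Day 42 | no |
| Day 56 | yes |
| Day 70 | no |
| Day 84 | no |
| Day 98 (EOS) | yes |
| ET | yes |

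That is five draws. Column alignment in the Table 8 row could not be relied on in the text available, but the row carries five marks, which fits. The Part A list for Day 84 (6.3.2.2) also omits the panel.

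**2. Distance from end of treatment, for completers**
- Last on-drug panel: 84 − 56 = 28 days before treatment ends, which is 28/84 = one third of the treatment period.
- Next panel: 98 − 84 = 14 days after the last dose. If the Day 84 visit moves by its 3-day window and Day 98 stays fixed, this is 98 − 87 = 11 to 98 − 81 = 17 days.
- In the 200 mg arm that dose runs from Day 15 to Day 84, which is 70 days. By the end of Day 56 the patient has had 56 − 14 = 42 of them, or 60%.

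**3. Markers affected**
- Named markers: 14, not counting the derived ELF score.
- Week 12 value from Day 84 chemistry: ALT, AST and their ratio, so 3.
- hs-CRP has a SAP Week 12 window (Days 71 to 91). Protocol Appendix B lists it only among the efficacy parameters, and no panel is scheduled on Day 84.
- No scheduled Week 12 draw: 14 − 3 = 11. With neither a draw nor a window: 14 − 4 = 10. These ten are adiponectin, interleukin 6, TNF-alpha, cytokeratin-18, fibronectin, hyaluronic acid, the type III procollagen peptide, TIMP-1, Pro-C3 and YKL-40. ELF is derived from markers in this set, so it has no Week 12 value either.

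**4. Group III windows** (SAP 3.1.4)
- Week 4 is Days 2 to 42, Week 8 is Days 43 to 77, and Week 14 is Day 92 onward.
- Days 78 to 91 belong to no visit. An ET sample taken then, days from the end of treatment, is not assigned to any analysis visit.

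**5. Patients affected**
- The planned completion rate is 26 of 30 per group (Protocol 10.2.8), so 3 × 26 = 78 completers and 90 − 78 = 12 early discontinuers. Protocol 6.5 provides an ET panel for the latter within 48 hours of the last dose.

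**The case against.** The strongest defence is that the schedule is deliberate and consistent. Protocol and SAP state the same Week 4, Week 8 and Week 14 time points. These are secondary markers in a Phase 2a trial, and the primary endpoint and its error control are untouched. On-drug values exist at Weeks 4 and 8, and cT1, itself a fibro-inflammatory measure, is imaged at Week 12. The words in SAP Section 5 can be read as covering only the markers that have a Week 12 window. All of this stands and limits the weight of the point. It does not supply an end-of-treatment value, and neither document gives a reason for leaving the panel out of a visit at which blood is already drawn.

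Four stronger readings are tempting, and the documents do not support them.

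- **That no marker is measured at Week 12.** ALT, AST and their ratio are.
- **That all 90 Part B patients lack an end-of-treatment value.** The gap concerns completers. Early discontinuers have an ET panel close to their last dose, though before Week 12.
- **That the Week 14/ET label pools on-drug ET samples with off-drug Week 14 samples.** SAP 3.1.4 assigns ET results by analysis day. Even with dosing to Day 87 and an ET visit 48 hours later, the sample falls by Day 89, before the Week 14 window opens at Day 92. ET visits after that are for patients who left after completing treatment, and they are off drug too.
- **That the drug's half-life shows the marker effect is gone by Week 14.** Protocol 1.1 says the half-life "was around 2 to 3 hours, with a tendency for faster elimination after multiple dosing". Fourteen days is then 14 × 24 / 3 = 112 to 14 × 24 / 2 = 168 half-lives. That shows clearance of the drug, not loss of effect on slower markers, and the documents give no turnover time for any marker. The figure also comes from healthy subjects, and Protocol 5.2 reports slower elimination in NASH.

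**Conclusion.** The point holds for completers. In about 78 patients at the planned completion rate, 10 or 11 of the 14 named markers (depending on how hs-CRP is counted), plus ELF, have no planned end-of-treatment value. The nearest samples are 28 days before and 14 days after the end of treatment. The effect at Week 12 on these markers cannot be estimated directly or paired with the Week 12 imaging. How much is lost depends on how quickly each marker responds and reverts, which is unknown.

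Separately, SAP Section 5 and the Group III windows need to be reconciled, and Days 78 to 91 need an analysis visit.

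The primary endpoint is not affected. This is an inexpensive improvement to a stated secondary objective. The conclusion rests on the visit-by-visit procedure lists being the operative schedule, and on no Laboratory Manual instruction adding the panel at Day 84. That manual was not available.

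**What to change.** - **Protocol 6.3.3.7 and Table 8:** add the panel to the Day 84 blood draw, and keep the Week 14 draw.
- **Protocol 7.1.2 and SAP 2.1.2:** name Week 12 as the end-of-treatment time point, and label Week 14 as off-drug follow-up.
- **SAP 3.1.4, Group III:** end Week 8 at Day 70 and add Week 12 as Days 71 to 91, as Group II already has. Adding the Week 12 window without shortening Week 8 would overlap on Days 71 to 77. Handle HbA1c separately, because SAP Section 5 excludes it at Week 12.
- **SAP Section 5:** say which markers have a Week 12 value and from which sample. State the source of hs-CRP.
- **Patients already past Day 84:** assay the stored plasma from that visit, provided matrix, volume and permitted use are confirmed. This may be a large share of Part B: the SAP puts completion of the interim analysis, triggered when half of Part B had completed Week 8, in February 2021, and the version 4.0 change entry is dated July 2021.

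The cost is up to about 90 extra assay panels (about 78 at the planned completion rate), with no extra visit. The downside is that Week 12 data will be incomplete if stored samples prove unsuitable. The study report should then say that no end-of-treatment value exists for those markers, and should not present Week 14 in its place.

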8 PHARMACOKINETIC AND PHARMACODYNAMIC ASSESSMENTS

Pharmacokinetic (EYP001a concentrations) and PD (C4 and FGF19 concentrations) data will be added to the current PK/PD database, and population PK/PD models will be reassessed to investigate potential influence of NASH on PK/PD relationships.

8.1 Pharmacokinetic Variables

In Part A, during the Safety Run-in Period, intense PK sampling will occur on Day 1 (± 1 day) and Day 14 (± 1 day) at the following timepoints: 0 (predose), 1, 2, 4, 6, 8, 10, 12, and 24 hours postdose; samples will be collected in the fasted state predose to 4 hours postdose, inclusive. Sparse PK samples will be collected for all other visits. Plasma samples to assess trough concentrations of EYP001a will be collected predose (fasting) in the morning and 2 hours postdose (an optional sample may also be collected at 6 hours postdose) at the following visits: Days 7, 21, 28, 56, and 84. A sample will also be collected at the EOS and ET Visits.

In Part B, sparse PK sampling will occur predose (fasting) at the following visits: Days 1, 14, 28, 56, and 84. A sample will also be collected at the EOS and ET Visits.

At the ET Visit (if applicable), the PK sample should be collected within 24 to 48 hours of last intake of study drug. The date and time of the PK draw and the last dose of study drug must be recorded in the eCRF.

Pharmacokinetic samples will be collected in a fasted state, defined as nothing by mouth except water for ≥ 6 hours, at all predose sampling timepoints (in Parts A and B) and at the 1- to 4-hour postdose timepoints (inclusive) on Days 1 and 14 of Part A. For BID dosing, PK timepoints will be based on the time of morning dosing.

8.2 Pharmacodynamic Variables

In Part A, intense PD sampling will occur on Day 1 (± 1 day) and Day 14 (± 1 day) at the following timepoints: 0 (predose, fasting), 4 (fasting), 6, 10, 12, and 24 hours postdose. Sparse PD sampling will also occur predose (fasting) and 2 hours postdose at the following visits: Days 28, 56, and 84. A sample will also be collected at the EOS and ET Visits.

In Part B, sparse PD sampling will occur predose (fasting) at the following visits: Days 1, 14, 28, 56, and 84. A sample will also be collected at the EOS and ET Visits.

At the ET Visit (if applicable), the PD sample should be collected within 24 to 48 hours of last intake of study drug. The date and time of the PD draw and the last dose of study drug must be recorded in the eCRF.

Pharmacodynamic samples will be collected in a fasted state, defined as nothing by mouth except water for ≥ 6 hours, at all predose sampling timepoints (in Parts A and B) and at the 4-hour postdose timepoint on Days 1 and 14 in Part A. For BID dosing, PD sampling timepoints will be based on the time of morning dosing.

Parameters will be measured in plasma samples using a validated method. Pharmacodynamic sampling will assess plasma levels of C4; FGF19; and total, primary, and secondary bile acids (such as chenodeoxycholic acid, deoxycholic acid, lithocholic acid, and/or others as appropriate).¹⁸

